### 4.1.6.2 Presentation

Baseline disease characteristic variables will be summarized for each treatment group and overall in the FAS population. Continuous variables will be summarized using n, mean, median, SD, minimum, and maximum; categorical variables will be summarized using number and percent of participants.

## 4.1.7 Medical History and Concomitant Disease

## 4.1.7.1 Definitions and Derivations

Complete medical history will include history and current medical conditions past or present, including cardiovascular (CV) disorders; respiratory, gastrointestinal, renal, hepatic, neurological, endocrine, lymphatic, hematologic, immunologic, dermatological, psychiatric, genitourinary, or any other diseases or disorders; drug and surgical history; and history of alcohol and tobacco use. Disease-related and relevant medical history are coded in Medical Dictionary for Regulatory Activities (MedDRA) version 25.0 or higher.

#### 4.1.7.2 Presentation

Relevant and disease-related medical history will be presented in summary tables as number and percentage of participants by System Organ Class (SOC) and Preferred Term (PT) for each treatment group and overall. Participants with multiple events in the same SOC/PT will be counted only once in that SOC/PT. Participants with events in more than 1 SOC/PT will be counted once in each of those SOC/PT. Tables will be sorted by international order for SOC and in alphabetical order for PT. The tables will be based on the safety population.

#### 4.1.8 Prior and Concomitant Medications

#### 4.1.8.1 Definitions and Derivations

The World Health Organization (WHO) Drug Dictionary March 2022 B3 Global or higher is used to classify medications by WHO Anatomical Therapeutic Chemical (ATC) classification of ingredients. Any medication or vaccine (including over-the-counter or prescription medicines, vitamins, and/or herbal supplements) that the participant is receiving at the time of enrollment or receives during the study will be recorded along with reason for use, dates of administration including start and end dates, and dosage information including dose and frequency.

Restricted and prohibited medications are described in the CSP. Potential prohibited and restricted CMs are identified by ATC code lists or flagged by the study physician.

For the purpose of analysis, prohibited medications will be determined as follows:

- Therapies associated with development of NAFLD such as methotrexate, tamoxifen, amiodarone, or long-term use of tetracyclines or systemic corticosteroids with start date < 90 days prior to date of biopsy used for screening. "Long-term use" is defined as a duration greater than 14 days.
- Therapies in classes under investigation for the treatment of NASH (except for SGLT-2 inhibitors), such as obeticholic acid, pioglitazone, and vitamin E with start date < 180 days prior to date of biopsy used for screening. In the case of pioglitazone or high-dose vitamin E, these drugs are restricted during the study unless the participant has been on a stable dose for at least 180 days prior to baseline biopsy (historical or on-study).

- Glucagon-like peptide-1 (GLP-1) receptor agonists and GLP-1 receptor agonist containing therapies with start date < 90 days prior to date of biopsy used for screening.
- Weight loss drugs with start date < 90 days prior to date of biopsy used for screening.
- Herbal preparations or dietary supplements marketed for control of body weight or appetite or with any suspected hepatotoxicity with start date < 14 days prior to first screening visit.
- In general, timing criteria will be assumed to be met for categorization as a prohibited medication when ambiguous due to missing information for start/end dates.

The imputation method described in Section 3.3.1 is used in case of medication stop date partially missing. Completely missing stop dates will not be imputed. Both completely missing and partially missing CM start dates are not imputed.

After the end date imputation, the medications will be classified as either prior or concomitant (but not both) according to its stop date. Prior medication is defined as any medication with a stop date prior to the first dose of study drug (exclusive). CM is defined as any medication with a stop date on or after the first dose of study drug, or any medication that is ongoing at study end. Medications with completely missing stop date are classified as concomitant.

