## **Prior/Concomitant Therapy**

16 Recent (within 90 days of screening biopsy or historical biopsy through screening) use of therapies associated with development of NAFLD (eg, methotrexate, tamoxifen,

- amiodarone, or long-term use of tetracyclines or systemic corticosteroids [inhaled, nasal, topical are allowed])
- 17 Recent (within 180 days of screening biopsy or historical biopsy through screening) use of obeticholic acid or other therapy under investigation for NASH
- 18 Pioglitazone or high dose vitamin E (> 400 IU) unless on a stable dose for at least 180 days prior to the baseline biopsy (either screening or historical) and not initiated after the biopsy was taken
- 19 Recent (within 90 days of screening biopsy or historical biopsy through screening) use of GLP-1 receptor agonist or GLP-1 receptor agonist containing therapies and weight loss medication(s) (approved and/or off-label use)

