# **6.5.2** Prohibited Concomitant Medications

Participants must be instructed not to take any medications, including NASH-related over-the-counter products, without first consulting with the investigator

Use of the following medications will be restricted (Table 9) or prohibited (Table 10) as specified:

**Table 9** Restricted Medications

Medication/class of drug:	Usage (including limits for duration permitted and special situations in which it is allowed ):
Systemic corticosteroids by oral, intravenous, or intramuscular route	Not to be used within 90 days prior to baseline biopsy (historical or screening) and during the study unless prescribed for a very brief period of less than 14 days
Prokinetic agents such as domperidone and metoclopramide	Only to be used during the study for the treatment of nausea and vomiting if a centrally acting antiemetic is deemed ineffective or not tolerated by the participant
Analgesics and antipyretics	Careful use of paracetamol (acetaminophen) is allowed, not to exceed 3 g/d

**Table 10** Prohibited Medications

Prohibited medication/class of drug:	Usage
Therapies associated with development of NAFLD such as methotrexate, tamoxifen, amiodarone, or long-term use of tetracyclines or systemic corticosteroids	Within 90 days prior to baseline biopsy (historical or screening) until the end of the study. Systemic corticosteroid and tetracycline use are restricted during the study unless prescribed for a very brief period of ≤ 14 days.
Therapies in classes under investigation for the treatment of NASH (except for SGLT-2 inhibitors), such as obeticholic acid, pioglitazone, and Vitamin E	Within 180 days of baseline biopsy until the end of the study. In the case of pioglitazone or high-dose vitamin E, these drugs are restricted during the study unless the participant has been on a stable dose for at least 180 days prior to baseline biopsy (historical or on-study). Potential drugs with new regulatory approvals for the treatment of NASH with fibrosis stage F2/F3 could be considered after discussion with study physician, if the investigator deems it not to be safe for the participant to postpone the start of such treatment until study end.
GLP-1 receptor agonists and GLP-1 receptor agonist containing therapies	Within 90 days of baseline biopsy (historical or onstudy) until the end of the study

**Table 10** Prohibited Medications

Prohibited medication/class of drug:	Usage

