Drugs approved for weight loss (eg, orlistat, bupropion/naltrexone, phentermine-topiramate, phentermine, lorcaserin), as well as those drugs used off-label	Concurrent or previous use within 90 days of baseline biopsy (historical or on-study) until the end of the study
Herbal preparations or dietary supplements marketed for control of body weight or appetite or with any suspected hepatotoxicity	Concurrent or prior use in the period starting within 14 days prior to the start of screening and for the duration of the study. Furthermore, starting new herbal preparations or dietary supplements of any kind is not allowed once screening activities are initiated.

GLP-1, glucagon-like peptide-1; NAFLD, non-alcoholic fatty liver disease; NASH, non-alcoholic steatohepatitis; SGLT-2, sodium-glucose co transporter 2

If any unintentional use of a prohibited medication occurs, consult with the AstraZeneca study physician for a case-by-case resolution.

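### SAP 4.1.8.1's herbal and supplement rule tests start date where protocol Table 10 tests use, so a listed product started 14 or more days before screening and continued is tabulated as non-prohibited

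*SAP*

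**What the plan says.** Protocol Section 6.5.2, Table 10, defines the prohibition for herbal preparations and dietary supplements that are marketed for weight or appetite control, or that have suspected hepatotoxicity, by use: "Concurrent or prior use in the period starting within 14 days prior to the start of screening and for the duration of the study". A separate sentence in the same row deals with starting: "starting new herbal preparations or dietary supplements of any kind is not allowed once screening activities are initiated".

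SAP Section 4.1.8.1 refers to the protocol for the description of prohibited medications, then sets its own rule for the analysis. In the herbal bullet a product of either named type counts if it falls under the phrase "or with any suspected hepatotoxicity with start date < 14 days prior to first screening visit". The bullet has no stop-date term.

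Three other statements in SAP 4.1.8.1 matter:

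- ATC code lists and study-physician flags pick out potential prohibited medications.
- Where missing dates leave the timing unclear, the timing criterion is taken as met.
- A medication is concomitant if it stops on or after first dose, is ongoing at study end, or has a completely missing stop date.

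SAP Section 4.1.8.2 then gives two tables in the safety population: concomitant medications without the prohibited ones, and prohibited concomitant medications. Both show ATC level 4 and product name.

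**The concern.** The two documents ask different questions about the same product. Table 10 asks whether it was used inside the window. The SAP asks whether it was begun inside the look-back or later. A product begun before the look-back and never stopped answers yes to the first and no to the second.

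At stake is whether the prohibited-medication table means what a reader will take it to mean. Safety is the primary objective and drug-induced liver injury is an adverse event of special interest. A reader of the liver results may use that table to see who took a product with suspected hepatotoxicity. By this route the table can omit such a participant.

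**Working it through.** **Setup.** Day 0 is the first screening visit. First dose was set at Day 21 and at Day 56 (the screening limit). Study end is first dose + 336 + 28 days. These are illustrative settings built from the protocol's period lengths; both gave the same classifications.

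- SAP flag: start later than Day -14, or start unknown.
- Table 10: the interval from start to stop overlaps Day -14 to study end.
- Concomitant: stop on or after first dose, or ongoing.

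| Start | Stop | SAP flag | Table 10 | Where it is counted |
|---|---|---|---|---|
| Day -30 | study end, or 100 days after first dose | no | yes | table without prohibited medications |
| Day -15 | study end | no | yes | table without prohibited medications |
| Day -14 | study end | no | yes | table without prohibited medications |
| Day -13 or -10 | study end | yes | yes | prohibited table |
| Day 0, or after first dose | study end | yes | yes | prohibited table |
| Unknown | ongoing | yes (fallback) | yes | prohibited table |
| Day -30 | Day -20 | no | no | prior medication, neither table |
| Day -30 | Day -5, or day before first dose | no | yes | prior medication, neither table |

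The rules part for every known start at Day -14 or earlier with continuation past first dose. The last row is also prohibited use under Table 10, but it is a prior medication and outside both tables whichever test is used.

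**Could the SAP wording be read otherwise?** The phrase could be taken to mean earlier than 14 days before screening. That would flag the Day -30 case but miss every start from Day -14 onward, including starts on study, so it cannot be intended.

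**Does anything else in the SAP correct it?** The ATC lists and physician flags identify candidates; the bullets then decide. The fallback needs missing information, and a known start of Day -30 is not missing. The fallback does mention end dates, which no bullet tests, so a use-based rule may have been meant.

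**The other bullets, same start-date form:**

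- GLP-1 agonist started 91 days before biopsy and ongoing (look-back 90): SAP no. Table 10 yes, its window being "Within 90 days of baseline biopsy (historical or onstudy) until the end of the study". But exclusion criterion 19 already bars "Recent (within 90 days of screening biopsy or historical biopsy through screening) use of GLP-1 receptor agonist", so this case needs an eligibility breach.
- NASH-class drug started 181 days before biopsy and ongoing (look-back 180): SAP no, Table 10 yes. Exclusion 17 covers therapies under investigation for NASH.
- Vitamin E started 400 days before biopsy, stable and ongoing: the start-date test flags no dose. An overlap test with only the existing stable-dose exception would exempt high dose and flag low dose.

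**Size.** About 55 randomized in 2:1:2:1.

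- Each cotadutide arm, or pooled placebo: 55 × 2/6 = 18.3. One participant: 100/18.3 = 5.5 points (100/17 = 5.9; 100/19 = 5.3).
- One unpooled placebo arm: 55 × 1/6 = 9.2. One participant: 55/6 = 9.17, and 100/9.17 = 10.9 points.
- All participants together: 100/55 = 1.8 points.
- 0 in the row for any prohibited medication if the participant already has another flagged one.

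**The case against.** A reader might infer that all five drug bullets are equally faulty. The documents do not support that. Exclusions 16, 17 and 19 bar the NAFLD-associated, NASH-class, GLP-1 and weight-loss drugs over the same look-backs through screening, and Section 5 permits no waivers. In an eligible participant, use of those classes on study must be a new start or restart, which the start-date test catches. The first two bullets also carry a duration and a stable-dose term. What stands is the herbal bullet: no numbered exclusion names herbal products or supplements, although one sold for weight control might be argued to fall under exclusion 19's weight-loss medication.

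A reader might also infer that SAP Section 2 wrongly fails to declare a departure. Section 2 concerns planned analyses, and protocol Section 9 plans no prohibited-medication table, so that inference is weak.

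A third inference is that any new supplement started on study is misclassified. Table 10's sentence on new products of any kind can be read as a rule of conduct rather than as defining a prohibited medication, and the text does not settle which.

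Finally, the consequence is small. The product stays visible by name in the other table, suspected liver injury is adjudicated case by case, and important deviations are listed under a Protocol Deviation Plan that is not among the documents. This holds, and it limits the point to a minor one. It does not make the two definitions agree.

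**Conclusion.** The mismatch is real for the herbal and supplement bullet. A listed product with a known start 14 or more days before screening, continued past first dose, is prohibited by Table 10 and tabulated by the SAP as not prohibited. For the GLP-1, weight-loss and NAFLD-associated bullets the same wording matters only if an eligibility criterion was breached.

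The size is one participant at a time: about 5.5 points in an arm of about 18, about 10.9 in an unpooled placebo arm of about 9, or 0 as noted. The by-arm figures assume display by arm, which SAP 4.1.8.2 does not state; pooling of placebo is stated only for the power comparison. No frequency is claimed.

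A reader might go further and expect the efficacy results or the per protocol set to shift. They do not. The histology estimand follows treatment policy for prohibited medication, and per protocol membership depends on biopsy, treatment duration and the excluded site. Severity is minor.

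**What to change.** In the herbal bullet of SAP 4.1.8.1, replace the start-date test with overlap between the medication's start-stop interval and the Table 10 window through end of study. Count an ongoing or missing stop date as overlapping.

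The same test can go into the GLP-1, weight-loss and NAFLD-associated bullets for consistency, keeping the duration test of more than 14 days.

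Leave the NASH-class bullet as it is until the vitamin E wording is reconciled. Table 10 names vitamin E without a dose, as does the SAP: "such as obeticholic acid, pioglitazone, and vitamin E with start date < 180 days prior to date of biopsy used for screening". Exclusion 18 is limited to "Pioglitazone or high dose vitamin E (> 400 IU) unless on a stable dose for at least 180 days prior to the baseline biopsy". The same review should settle how this table counts drugs taken under Table 10's provision: "Potential drugs with new regulatory approvals for the treatment of NASH with fibrosis stage F2/F3 could be considered after discussion with study physician".

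The sponsor should also reconcile whether Table 10's sentence on new products of any kind defines a prohibited medication for this table or is a conduct rule handled as a protocol deviation.

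The cost is a wording change in one bullet (four if aligned), one interval condition in the program, and two sponsor decisions. Start and stop dates, dose and frequency are already collected. No drug list, window or clinical rule changes.

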#### 4.1.8.2 Presentation

The number and percentage of participants with at least 1 CM (excluding prohibited medications) and the number and percentage of participants by ATC level 4 (therapeutic subgroup) and product name will be provided using the Safety population.

The number and percentage of participants with at least 1 prohibited CM and the number and percentage of participants by ATC level 4 (therapeutic subgroup) and product name will be provided using the Safety population by period.

# 4.1.9 Study Drug Compliance

## 4.1.9.1 Definitions and Derivations

When participants are dosed at the site, they will self-administer the study intervention under medical supervision from the investigator or designee. The date and time of dose administered in the clinic will be recorded in the source documents and in the eCRF.

While the number of returned pens is counted, pens will not otherwise be inspected for compliance.

#### 4.1.9.2 Presentation

Given the limitations in data collection, study drug compliance will not be summarized.

# 4.2 Endpoint Analyses

The primary analyses will be of safety. No formal hypothesis testing will be performed. Treatments will be compared in tables using descriptive statistics. All efficacy analyses are exploratory.

# 4.2.1 Primary Endpoint

The primary objective is to evaluate the safety and tolerability of cotadutide as compared with placebo in participants with non-cirrhotic NASH with fibrosis.

Primary safety endpoints:

Safety and tolerability will be evaluated in terms of AEs, vital signs, clinical and laboratory assessments, and ECGs.

Assessments related to AEs cover:

- Occurrence/frequency
- Relationship to IP as assessed by the investigator
- Intensity
- Seriousness
- Death
- AEs leading to discontinuation of IP
- AEs leading to dose reduction of IP
- AEs of special interest
- Adjudicated CV events including major adverse cardiovascular event (MACE), selected liver events, diabetic ketoacidosis, pancreatitis, pancreatic carcinoma, and thyroid carcinoma

Vital signs parameters include SBP, diastolic blood pressure (DBP), and pulse.

Assessments cover:

- Observed value
- Absolute change from baseline values over time
- Abnormality at least once on treatment

Laboratory parameters include clinical chemistry (including MELD score) and hematology parameters as well as urinalysis.

#### Assessments cover:

- Observed value
- Absolute change from baseline values over time
- Abnormality/clinically significant abnormality in laboratory parameters at least once on treatment
- Treatment-emergent increase in hematuria, proteinuria, and glucose in urinalysis defined as change from negative/trace at baseline to ++, +++, or ++++ at any visit after baseline or an increase of at least ++

Electrocardiogram measurements include heart rate, RR, PR, QRS, and QT intervals. Derived variables cover OTcF.

#### Assessments cover:

- Observed value
- Absolute change from baseline values over time
- ECG parameters fulfilling potentially clinically significant criteria at any time during treatment, including QRS duration > 118 ms, PR interval > 210 ms, RR < 600 ms (resting heart rate > 100 bpm), and RR > 1330 ms (resting heart rate < 45 bpm)
- QTcF exceeding 450, 480, and 500 ms at any time during treatment
- Change in QTcF at any time during treatment as compared to baseline exceeding 30 ms and 60 ms

For details of the safety analysis, refer to Section 4.5.

A second primary objective is 'to assess the immunogenicity of cotadutide' with associated endpoint "incidence of ADAs to cotadutide and titer during treatment and follow-up." Details of analysis of anti-drug antibodies (ADAs) can be found in Section 4.4.

# 4.2.2 Secondary Endpoints

There are no secondary endpoints.

## 4.2.3 Other Endpoints

#### 4.2.3.1 Definition

Tertiary/exploratory endpoints will be tested versus placebo at the 2-sided nominal alpha 5% level, without consideration of multiplicity:

The following are histological endpoints, to be assessed centrally 1) by independent pathologists and 2) by artificial intelligence, as detailed in the Central Histopathology Review

Charter. Analysis of continuous histological scores, if included, will be based solely on values provided by artificial intelligence.

- Proportion of participants with resolution of NASH without worsening of liver fibrosis based on biopsy at Week 48
- Proportion of participants with improvement of liver fibrosis by at least 1 stage without worsening of NASH based on biopsy at Week 48. (Worsening of NASH is defined as any increase in the ballooning, inflammation, or steatosis scores even if total NAS does not increase.)
- Proportion of participants with both resolution of NASH and improvement in fibrosis by at least 1 stage based on biopsy at Week 48
- Proportion of participants with improvement in fibrosis by at least 1 stage based on biopsy at Week 48
- Proportion of participants with improvement in NAS based on biopsy at Week 48
- Change from baseline in NAS based on biopsy at Week 48
- Change from baseline in fibrosis stage based on biopsy at Week 48
- Proportion of participants with progression, no change, or regression in fibrosis stage based on biopsy at Week 48
- Proportion of participants with improvement in key histological features of NASH on biopsy at Week 48, including:
  - Inflammation
  - Steatosis
  - Ballooning

Below are other exploratory/tertiary endpoints not based on biopsy:

- Change from baseline in liver enzymes including ALT and AST through Week 48
- Change from baseline in triglycerides, LDL cholesterol, and HDL cholesterol, non-HDL cholesterol, and total cholesterol, and HbA1c through Week 48
- Cotadutide PK exposure will be summarized and compared with prior data for consistency
- Change from baseline at Week 48 in:
  - LSM as assessed by FibroScan
  - Percentage CAP as assessed by FibroScan
- Changes from baseline at Week 48 in non-invasive disease-specific biomarkers, including but not limited to:
  - Pro-C3

- ELF score
- FIB-4
- APRI
- NFS
- BARD score
- FAST score
- Agile 3+
- Percent change from baseline in body weight at Week 48
- Change from baseline in FPG, adiponectin, and C-peptide at Week 48
  - Both total and high molecular weight adiponectin will be assessed
- Change from baseline in SBP through Week 48

